**Table BDCM.2. Objectives and Endpoints**

Objectives	Endpoints
Primary 
 
To investigate the efficacy of LY3209590 arms in study participants with T2DM
 
	
 
HbA1c change from baseline to Week 32
 

Secondary Efficacy 
 
To investigate the efficacy of LY3209590 compared with insulin degludec in study participants with T2DM.
 
	
 
HbA1c change from baseline to Week 12 and 32
 
Fasting glucose change from baseline to Weeks 12 and 32
 
Insulin dose change from baseline to week 12 and 32
 

Safety 
 
To investigate the safety of LY3209590 compared with insulin degludec in study participants with T2DM.
 
	
 
Incidence and rate of hypoglycemia
 
Incidence and rate of nocturnal hypoglycemia
 
Incidence and rate of severe hypoglycemia
 
Incidence of treatment-emergent serious AEs
 
Body weight change from baseline at Weeks 12 and 32
 

Pharmacokinetics 
 
To characterize the PK of LY3209590 in study participants with T2DM
 
	
 
LY3209590 population-based parameters, such as, AUC within dosing interval at Weeks 12 and 32
 

Exploratory 
 
To investigate the safety and tolerability of LY3209590 compared with insulin degludec in study participants with T2DM.
 
	
 
Treatment-emergent AEs
 
Discontinuation of IP due to AEs
 
Clinical laboratory results
 
Systematic assessment of injection site reactions
 
Insulin dose during follow up period
 
Incidence and rate of hypoglycemia during treatment and follow-up period
 
Incidence and rate of daytime hypoglycemia
 
Liver aminotransferase change from baseline to Weeks 12 and 32
 

 
To explore quality of glycemetic control compared with insulin degludec using CGM
 
	
 
Glucose time in target range, time in hyperglycemia, time in hypoglycemia
 
Duration and recurrence of hypoglycemic events
 

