### **10.3.3. Efficacy Analyses**

#### **10.3.3.1. Primary Analyses**

The primary efficacy outcome is HbA1c change from baseline to Week 32 for LY arms. The mixed-effect model repeated measures (MMRM) with BMI strata, treatment, visit, SU (Y/N), and treatment-by-visit interaction as fixed effects, HbA1c baseline as a covariate will be used for the analysis. The within-study participant correlation will be modelled through a variance-covariance structure. The dependent variable will be the post-baseline change from baseline values. The unstructured covariance matrix will be selected initially. There will be no explicit missing data imputation as the missing values are handled implicitly by the MMRM model.

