#### **10.3.3.2. Secondary Analyses**

The secondary analysis will be performed on the efficacy analysis set. The main secondary efficacy analysis aims to compare LY versus Insulin Degludec with regarding to HbA1c change from baseline at Week 12 and 32. The estimand of interest is the treatment differences in HbA1c at 12 and 32 weeks while the study participants are on study treatment. The efficacy analysis set (EAS) will be used to calculate the mean difference between treatments. Similar MMRM model will be used for the main secondary analysis. The least-squares (LS) mean differences and the standard errors from each imputed sample will be calculated based on the above model, and the final estimation for the means, standard errors, 90% confidence intervals, and p-values will be reported.

A supplementary analysis will be conducted to evaluate the “treatment policy” estimand, which is defined as the treatment differences in HbA1c at 32 weeks with the randomized treatment based on FAS. The estimator is defined as the mean difference between treatments based on FAS. The missing values will be imputed using multiple imputations. The similar MMRM model will be performed on imputed data and inferences will be drawn based on the framework of multiple imputations (Rubin, 1987).

In addition to the main secondary efficacy analysis of HbA1c, the following secondary efficacy outcomes will be analyzed:

- Body weight and change from baseline to 12 and 32 weeks
- Fasting blood glucose and change from baseline at 12 and 32 weeks

The analyses of the HbA1c change, mean weight change, fasting blood glucose change and SMBG change from baseline will be conducted through MMRM similar to that of the primary efficacy outcome. The corresponding baseline will be used in the model instead of the baseline HbA1c levels. The MMRM model will also include a term for the HbA1c stratification group. The treatment p-value will be used as evidence of difference between LY3209590 and insulin degludec, while the comparison of LS means versus insulin degludec (unadjusted for multiple comparisons) and its 90% confidence interval will provide magnitude and significance of this difference.

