### 10.3.4. Safety Analyses

The FAS will be used for safety analyses. Both the overall and the pairwise comparisons of each LY3209590 arm versus insulin degludec will be reported for these safety analyses.

Safety measures include liver biomarkers (ALT), hypoglycemia, vital signs (BP and pulse rate), body weight, TEAEs (including SAEs and AEs of special interest), laboratory measures (including anti-LY3209590 antibodies), and ECGs. Summary statistics will be presented by treatment for the safety measures.

The summary statistics for continuous variables will be sample size, mean, SD, median, minimum, and maximum.

The summary statistics for categorical variables will be sample size, frequency, and percentage.

Exposure to each therapy during the treatment period of the study will be calculated for each study participant and summarized by treatment group.

In addition, the following safety outcomes will be analyzed on the efficacy analysis set population:

- ALT change from baseline to 12 and 32 weeks

The change from baseline of ALT will be analyzed using MMRM model. In addition, Bayesian model will be used to conduct the same analysis. The corresponding baseline will be used in the model instead of the baseline HbA1c levels. The MMRM model will also include a term for the HbA1c stratification group.

Additional analyses, such as concentration-safety laboratory plots, may be performed, if warranted upon review of the data.

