4.10.3.2. Hypoglycemia Events.....	14
4.10.3.3. Hepatobiliary Events.....	15
4.10.3.4. Injection Site Reactions.....	16
4.10.3.5. Systemic Hypersensitivity Reaction.....	17
4.10.4. Laboratory Measures.....	18
4.10.4.1. Lipid Measures.....	19
4.10.4.2. Liver Enzyme Elevation Measures.....	19
4.10.5. Vital Signs and Body Weight.....	20
4.10.6. Antibodies.....	21
4.10.6.1. Anti-LY3209590 Antibodies.....	21

4.10.7. Electrocardiograms	22
4.11. Continuous Glucose Monitoring Analysis	22
4.11.1. General Consideration.....	22
4.11.2. CGM Variable and Analysis.....	22
4.11.2.1. Hypoglycemia	23
4.11.2.2. Hyperglycemia	23
4.11.2.3. Normal Range	23
4.11.2.4. Glycemic Variability	23
4.11.3. Definition of Variables.....	24
4.11.3.1. Glucose in Target Ranges, Hypoglycemia or Hyperglycemia	24
4.11.3.2. Hypoglycemic Episode.....	24
4.11.3.3. Glycemic Variability	24
4.12. Subgroup Analyses.....	27
4.13. Interim Analyses	27
5. Unblinding Plan	29
6. References	30

Table of Contents

Table		Page
Table BDCM.1.	Hypoglycemia Event Related Analyses.....	15
Table BDCM.2.	List of MedDRA Preferred Terms (PTs) to Search for Injection Site Reaction Adverse Events (AEs).....	17
Table BDCM.3.	Categorical Criteria for Abnormal Treatment-Emergent Blood Pressure and Pulse Measurement.....	21

Revision History

Statistical Analysis Plan (SAP) Version 1 was approved on 31 January 2019. Version 1 was based on the Protocol I8H-MC-BDCM approved on 31 August 2018.

This SAP is the second version approved prior to the final database lock. The main changes are listed below:

- Correcting mistakes in the first version (for examples, MMRM model terms for the primary and secondary outcome, and significant level for treatment effect tests)
- Removing duplicated information/analysis in the same section to avoid confusion
- Updating analysis details to be consistent with other Phase 2 studies in the same program (for example, the definition of Safety Population)
- Replacing the multiple imputation method for the analysis of HbA1c meeting the target with longitudinal logistic regression
- Adding required safety analyses which were missing in the first version (for example, analysis of body weight and analysis of treatment emergent antidrug antibody status)
- Providing analysis details to clarify the analysis input data (for example, the SMQ search criteria for hepatobiliary events)

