3.2.2. Safety

To compare the safety of LY3209590 versus insulin Degludec treatment groups for the following:

1. Documented, documented nocturnal and severe hypoglycemia incidence and rates during the treatment period (0-12, 12-32, and 0-32 weeks);
2. Treatment-emergent serious adverse events (SAEs) incidences;
3. Body weight change from baseline at Week 12 and 32.

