4.10.5. Vital Signs and Body Weight

Vital signs and weight will be summarized by treatment and visit. Change from baseline (last nonmissing value up to Visit 3) to postbaseline value for vital signs and weight will be summarized for patients who have both a baseline and at least 1 postbaseline result.

Treatment differences in mean change will be assessed using MMRM. The MMRM model will be used for the analysis during the treatment period and will contain the terms for treatment, baseline value, visit, and visit-by-treatment interaction as factors; patient as random effect; and CS as the variance-covariance structure. Only scheduled measures will be included in the MMRM analyses.

The percentages of patients with treatment-emergent high or low vital signs at any time after randomization will be summarized and compared between treatment groups using Fisher's exact test. A treatment-emergent high result is defined as a change from a value less than or equal to the high limit (140 mm Hg for systolic blood pressure, 90 mm Hg for diastolic blood pressure, and 100 bpm for pulse) at baseline to a value greater than the high limit at any time that meets the specified change criteria after randomization. A treatment-emergent low result is defined as a change from a value greater than or equal to the low limit (90 mm Hg for systolic blood pressure, 50 mm Hg for diastolic blood pressure, and 50 bpm for pulse) at baseline to a value less than the low limit at any time that meets the specified change criteria after randomization. Patients with missing baseline measures will be excluded from this analysis unless otherwise specified. Scheduled visits, unscheduled visits, and retest measurements will be included in this analysis. [Table BDCM.3](#) will be used to define the low and high limits and change thresholds.

Table BDCM.3. Categorical Criteria for Abnormal Treatment-Emergent Blood Pressure and Pulse Measurement

Parameter	Low	High
Systolic BP (mm Hg) (Supine or sitting)	≤ 90 and decrease from baseline ≥ 20	≥ 140 and increase from baseline ≥ 20
Diastolic BP (mm Hg) (Supine or sitting)	≤ 50 and decrease from baseline ≥ 10	≥ 90 and increase from baseline ≥ 10
Pulse (bpm) (Supine or sitting)	< 50 and decrease from baseline ≥ 15	> 100 and increase from baseline ≥ 15

Abbreviations: BP = blood pressure; bpm = beats per minute.

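### Body weight change, a secondary endpoint, gets a fixed compound-symmetry model without strata in SAP 4.10.5, where protocol 10.3.3.2 calls for a primary-type MMRM; the SAP gives no reason

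*SAP*

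**What the plan says.** Both documents make weight a secondary endpoint, filed under safety: "Body weight change from baseline at Weeks 12 and 32" in protocol Table BDCM.2 and "Body weight change from baseline at Week 12 and 32" in SAP 3.2.2. Protocol 10.3.4 also names it as a safety measure ("Safety measures include liver biomarkers (ALT), hypoglycemia, vital signs (BP and pulse rate), body weight").

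The only protocol text that specifies a model for weight is 10.3.3.2, where weight also appears among the secondary efficacy outcomes. The analyses of "mean weight change, fasting blood glucose change and SMBG change from baseline will be conducted through MMRM similar to that of the primary" outcome, with the matching baseline and an added HbA1c stratum. The primary model in protocol 10.3.3.1 has BMI strata, sulfonylurea use, treatment, visit, their interaction and baseline. On covariance it says: "The unstructured covariance matrix will be selected initially".

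SAP 4.7 uses that type of model for HbA1c: strata for country, BMI and sulfonylurea use, unstructured covariance, six ordered fallbacks and Kenward-Roger degrees of freedom. SAP 4.8 carries it to fasting glucose and the SMBG outcomes with the HbA1c stratum added. Weight is not in that list. SAP 4.10.5 models weight together with vital signs, using treatment, baseline, visit and "visit-by-treatment interaction as factors; patient as random effect; and CS as the variance-covariance structure". The revision history describes the weight analysis as an addition ("Adding required safety analyses which were missing in the first version (for example, analysis of body weight" is its example) and mentions alignment with other Phase 2 studies in the program. It says nothing about the covariance.

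**The concern.** Fasting glucose and weight stand in the same protocol sentence. The SAP follows that sentence for one and not for the other.

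The covariance is the part that can affect validity. SAP 4.7 lists compound symmetry with and without heterogeneous variances as separate structures, so an unqualified CS most naturally means equal variances, although 4.10.5 does not say so. Under that form one variance, pooled over all visits, sets the standard error at each of them. No robust standard error is stated. If the spread of weight change differs by visit, the interval at Week 32, one of the two named time points, has the wrong width.

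Protocol 5.4 names weight gain as one of the effects on which the new insulin is to be compared with degludec. At stake are the 90% interval and p-value of that comparison.

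**Working it through.** **The plan's own figure.** The only power figure concerns HbA1c (protocol 10.1): 200 versus 100 completers, margin 0.4, SD 1.1, true difference 0, two-sided alpha 0.10. 0.4 / (1.1 × √(1/200 + 1/100)) = 2.969, and Φ(2.969 − 1.645) = 0.907, against a stated 90%. It reproduces and does not depend on the weight model. No figure is given for weight.

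**Inputs for weight.** Two-sided alpha 0.10 (SAP 4.1); 125 per arm and 20% dropout (protocol 10.1). Assumed: weight visits at Weeks 3, 6, 12, 18, 28 and 32, read from a schedule table that is broken in the text; and the SD of weight change, which the documents do not give, changing either linearly with week or as a power of week. The Week 32 to Week 3 SD ratio runs from 0.8 to 2.

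**Formula (complete, balanced data).** With a visit-by-treatment term, the estimate at each visit is the difference in means at that visit. Its true variance uses that visit's SD, and equal-variance CS substitutes the mean variance over visits:

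- SE ratio (CS / true) at visit t = √(mean visit variance / variance at t)
- actual two-sided error = 2 × [1 − Φ(1.645 × SE ratio)]

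**Worked case, linear growth, ratio 1.25.** SDs relative to Week 3 are 1, 1.026, 1.078, 1.129, 1.216 and 1.25. Mean variance = 1.255. At Week 32, √(1.255 / 1.5625) = 0.896 and the error is 14.0%. At Week 12, √(1.255 / 1.161) = 1.040 and the error is 8.7%.

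| SD ratio, Week 32 : Week 3 | Week 32 SE ratio (linear; power) | Week 32 error | Week 12 error |
|---|---|---|---|
| 0.8 | 1.137; 1.101 | 6.1-7.0% | 9.9-11.1% |
| 1 | 1; 1 | 10% | 10% |
| 1.25 | 0.896; 0.919 | 13.0-14.0% | 8.7-9.7% |
| 2 | 0.756; 0.799 | 18.9-21.4% | 5.8-8.0% |

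So the Week 32 interval is 8-10% too narrow at ratio 1.25 and 20-24% too narrow at ratio 2.

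**Other visit sets.** Dropping Week 18, dropping Week 28 or adding Week 24 gives Week 32 errors of 12.7-14.8% at ratio 1.25 and 17.9-23.9% at ratio 2. The Week 12 direction is not fixed: without Week 28 and with power growth, the error at ratio 1.25 is 10.2%.

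**Simulation.** 3,000 trials per scenario, 3 × 125, linear SD, one LY3209590 arm versus degludec at Week 32. The two CS rows differ in correlation as well as dropout: constant 0.8 in the first, 0.95^(weeks apart / 3) in the second.

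| SD ratio | 0.8 | 1 | 1.25 | 1.5 | 2 |
|---|---|---|---|---|---|
| CS, no dropout | 6.5% | 10.5% | 14.3% | 16.2% | 21.7% |
| CS, serial correlation, 20% dropout | 6.8% | 10.4% | 16.8% | 18.1% | 23.8% |

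Unstructured covariance stayed at 9.4-11.1% throughout. Monte Carlo SE is about 0.5 points at 10% and 0.8 at 22%.

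**Omitted strata.** SE ratio = √(1 / (1 − R²)): 1.005 if the strata explain 1% of the variance and 1.054 if they explain 10%. The interval widens slightly; validity is not lost.

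**Liver baseline (separate minor point).** Protocol 10.3.1 averages three assessments for ALT, AST and GGT, and protocol 10.3.4 puts the HbA1c stratum in the ALT model. SAP 4.1 and 4.10.4 use the last single value and no stratum. Let rb be the correlation among baseline draws and rw that of a draw with Week 32. Residual variance is 1 − rw² with one draw and 1 − 3rw² / (1 + 2rb) with the mean of three. At rb 0.8 and rw 0.6: 0.640 versus 0.585, a 9% cut (SE 4% smaller). At 0.8 and 0.8: 0.360 versus 0.262, a 27% cut (SE 15% smaller). For rb 0.6-0.9 and rw from 0.4 up to rb, the cut is 1-30%.

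**The case against.** **The change is allowed.** Protocol 10.3.1 and SAP 4.1 let the SAP alter non-principal methods, with the reason given in the SAP or the study report. The report is not available here. This stands: the SAP states no reason, but that does not show that none exists.

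**The protocol wording is loose, and weight fits the common safety model.** The protocol says similar, and says unstructured only initially. The same CS model serves laboratory tests, vital signs and ECG. As a choice of layout this is coherent. It does not make an equal-variance interval right at Week 32 when SDs differ by visit. Weight also differs from those measures in being a secondary endpoint whose model protocol 10.3.3.2 spells out.

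**The size is assumed.** True. The range includes no harm and a conservative error.

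Four stronger readings are tempting and are not supported:

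- *That the lack of a fallback order is a defect.* Plain CS is already the last and simplest of the six fallbacks in SAP 4.7.
- *That the analysis population is unsettled.* The protocol does point two ways: 10.3.3.2 says "The secondary analysis will be performed on the efficacy analysis set", while 10.3.4 uses the full analysis set. SAP 4.1 and 4.10 settle it on the Safety Population, and 4.10.5 limits the model to the treatment period and scheduled measures. Only one detail stays open: whether scheduled visits after stopping drug but before Week 32 enter the model.
- *That the Week 32 interval will be too narrow, or the Week 12 interval always too wide.* Without weight SDs neither can be said.
- *That the strata or the liver baseline threaten validity.* Both cost precision only, and liver enzyme change is exploratory.

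**Conclusion.** The concern holds as an unexplained departure from the protocol's model for a secondary endpoint, with a possible but unquantified effect on the Week 32 interval. If CS means equal variances, actual error at nominal 10% is about 6-7%, 10%, 13-14% and 19-21% for SD ratios of 0.8, 1, 1.25 and 2. These figures rest on assumed SDs and on visit weeks read from a broken table; they are a range, not estimates for this trial. The Week 12 effect is smaller, and its direction depends on the visit set and growth pattern. Unstructured covariance does not depend on equal SDs.

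The reach is limited: this is one secondary endpoint in an open-label Phase 2 study, with no margin or decision rule on weight. The change is worth making because it costs almost nothing, not because a main conclusion is at risk.

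**What to change.** In SAP 4.10.5, for body weight only:

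- Use the Section 4.7 model with baseline weight in place of baseline HbA1c: treatment, visit, their interaction, country, BMI stratum and sulfonylurea use, plus the HbA1c stratum (<8.5%, ≥8.5%). Country is in the SAP 4.7 model but not in protocol 10.3.3.1; including it keeps weight in line with the SAP's other primary-type models.
- Use unstructured covariance with the 4.7 fallback order and Kenward-Roger degrees of freedom. Delete the patient random effect and CS for weight; if CS is placed on the residuals, the two are redundant anyway.
- Keep the Safety Population and the existing limits to the treatment period and scheduled measures. Add one sentence on whether scheduled visits after drug discontinuation but before Week 32 are included.
- If CS is kept, say whether variances are equal and give the reason.

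Separately, in SAP 4.10.4: for the ALT, AST and GGT models use the average of the three pre-randomization assessments as baseline, stating whether it is taken before or after the log transformation, and add the HbA1c stratum to the ALT model. The maximum-baseline categories in 4.10.4.2 can stay.

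Cost: SAP wording and reuse of the 4.7 code, with no new data. The downside is an occasional fallback to a simpler covariance if the unstructured fit does not converge.

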4.10.6. Antibodies

4.10.6.1. Anti-LY3209590 Antibodies

The sample to determine antibody against LY3209590 will be collected at protocol-specified visits. Treatment emergent antidrug antibodies (TEADA) can be subclassified as either treatment induced (baseline antibody level is not detected) or treatment boosted (baseline antibody level is detected):

- treatment induced response: a titer 2-fold (1 dilution) greater than the minimum required dilution (1:20) if the baseline level is not detected (i.e., titer less than the minimum required dilution)
- treatment boosted response: a 4-fold (2dilution) increase in titer compared to baseline if the baseline level is detected. For an example, 1:20 at baseline and 1:80 post baseline is treatment boosted.

The TEADA status will be determined by all postbaseline data. The number and percentage of patients with positive TEADA response any time after randomization including the treatment period and follow-up period will be summarized by treatment group.

A listing of anti-LY3209590 antibodies at each visit will be provided for the safety population. The listing will include anti-LY3209590 antibody status (detected/not detected), the titer for detected samples.

4.10.7. Electrocardiograms

Electrocardiograms (ECGs) will be collected at specific study visits. For screening visit, a single ECG will be collected. For the other scheduled visits, a triplicate ECG will be performed and the average values will be used in the analysis.

The actual and change from baseline for selected ECG parameters (heart rate, PR auto global beat, QRS, QT and QTcF) will be analyzed using the MMRM model. The MMRM model will be used for the analysis during the treatment period and will contain the term for treatment, baseline value, visit, and visit-by-treatment interaction as factors, patient as random effect, and compound symmetric as the variance-covariance structure.

4.11. Continuous Glucose Monitoring Analysis

4.11.1. General Consideration

The continuous glucose monitoring system will be offered to all patients at selected sites in Study I8H-MC-BDCM. Interstitial glucose (ISIG) values will be collected by the CGM at 5-minute intervals. Continuous glucose monitoring recordings will be obtained for all patients throughout the treatment phase of the study. The device readings and alarms will not be blinded to the patients so that they can be warned of hypoglycemia and appropriately manage any hypoglycemic episodes.

All patients who are randomized to 1 of the study treatments (LY3209590 Algorithm 1, LY3209590 Algorithm 2, insulin degludec) receive at least 1 dose of study treatment, and have CGM data from at least 1 collection period which will be included in the analyses. The data collected after permanent discontinuation of investigational product will be censored. There will be no multiplicity adjustment. Since the sensor takes about 2 hours to reach the steady state after insertion, it is recommended to only use the steady state data for analysis.

Summary statistics will include the number of observations, mean, median, maximum, minimum, and SD for all continuous measures. For categorical measures, the number of observations, proportion, and frequencies will be included in summary statistics. All analyses will be performed for data collected by visit and treatment.

